6.3.2 Study follow-up

Both as-treated (AT) and intention-to-treat (ITT) analyses will be conducted with treatment defined as the index drug on the day of cohort entry. Because adherence in the real world databases is expected to be much worse than in the trial, the AT analysis is the **primary** analysis, as it targets the relative hazard of outcomes on treatment.

For the AT analyses, the follow-up will start the day after initiation of linagliptin and comparator and will continue until the earliest date of the following events:

- The first occurrence of the outcome of interest, unless otherwise specified for selected outcomes,
- The date of end of continuous registration in the database,
- End of the study period,
- Measured death event occurs,
- Nursing home admission

- Nursing home admissions are considered a censoring event because the data sources utilized typically provide little to no data on a patient, particularly on drug utilization, after admission. We will utilize this as an exclusion reason for cohorts for the same reason.
- The date of drug discontinuation, defined as the date of the last continuous treatment episode of the index drug (linagliptin and comparator) plus a defined grace period (i.e., 30 days after the end of the last prescription's days' supply in main analyses).
- The date of augmentation or switching from an exposure to a comparator or any other agent in the comparator class and vice versa (e.g. switching from glimepiride to glipizide would be a censoring event);
 - A dosage change on the index treatment does not fulfill this criterion
 - An added treatment that is not part of the exposure or comparator group does not fulfill this criterion (e.g. if a linagliptin user adds insulin, he or she does not get censored at the time of insulin augmentation)

For the ITT analyses, the censoring based on the augmentation/switching and treatment discontinuation will be replaced with a maximum allowed follow-up time of 365 days.

7. Initial Feasibility Analysis

Action report links:

Optum: <https://bwh-dope.aetion.com/#/projects/details/702/results/30636/result/0>

Marketscan: <https://bwh-dope.aetion.com/#/projects/details/701/results/30634/result/0>

Medicare: <https://bwh-dope.aetion.com/#/projects/details/703/results/30635/result/0>

Date conducted: rerun on January 28, 2019

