After review of initial feasibility and power analyses, complete creation of the remaining covariates (see Table 1 below for list of covariates). Again, using the dummy outcome of a 90-day gap in database enrollment, complete a 1:1 PS-matched analysis. The PS should include the complete list of covariates (excluding laboratory values, which are missing in some patients).

- Provide plot of PS distributions stratified by treatment group.

Note- Please refer to **Appendix B**.

- Report covariate balance after matching.

Note- For Table 1, please refer to **Appendix B**.

- Report reasons for censoring by treatment group.

	Overall	Referent	Exposure
Dummy Outcome	0 (0.00%)	0 (0.00%)	0 (0.00%)
Death	1,704 (1.67%)	929 (1.82%)	775 (1.52%)
Start of an additional exposure	4,752 (4.67%)	746 (1.47%)	4,006 (7.87%)
End of index exposure	58,792 (57.74%)	29,602 (58.14%)	29,190 (57.33%)
Specified date reached	18,168 (17.84%)	9,825 (19.30%)	8,343 (16.39%)
End of patient enrollment	9,190 (9.02%)	4,583 (9.00%)	4,607 (9.05%)
Switch to other SUs (for censoring) + nursing home admission	9,224 (9.06%)	5,230 (10.27%)	3,994 (7.84%)

- Report follow-up time by treatment group.

Patient Group	Median Follow-Up Time (Days) [IQR]		
	Optum	MarketScan	Medicare
Overall Patient Population	118 [58-286]	128 [63-304]	137 [65-323]
Referent	122 [65-304]	148 [86-344]	148 [86-344]
Exposure	118 [58-269]	127 [58-303]	127 [58-303]

- Report overall risk of the primary outcome.

	Optum	Marketscan	Medicare
Risk per 1,000 patients	16.55	18.7	42.47

10. Final Power Assessment

Date conducted: 12/01/2019

- Re-calculate power in the appropriate excel table, using the revised number of matched patients from the PS-match in Section 9. All other parameters in the table should be the same as in Section 8. If the study is to be implemented in more than one database, copy and paste excel sheet to report power for each database separately and for the pooled analysis that uses data from all databases together. Power calculations are based on the formulas from Chow et al. (2008).

- Pooled

Non-inferiority Analysis	
Number of patients matched	
Reference	50,915
Exposed	50,915
Risk per 1,000 patients	25.91
Assumed HR from RCT	1
Alpha (2-sided)	0.05
Non-inferiority margin	1.3
Number of events expected	2638.4153
Power	0.999999116

- Optum

Non-inferiority Analysis	
Number of patients matched	
Reference	8,880
Exposed	8,880
Risk per 1,000 patients	16.55
Assumed HR from RCT	1
Alpha (2-sided)	0.05

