
II. Evidence of impaired renal function with predefined UACR, with or without CV co-morbidities, defined as follows (and/or criteria):
 
 - Impaired renal function (as defined by MDRD formula) with an eGFR: 15-<45 mL/min/1.73 m² at visit 1 (screening) with any UACR. - Impaired renal function (as defined by MDRD formula) with an eGFR ≥ 45-75 mL/min/1.73 m² at visit 1 (screening) with an UACR > 200 mg/g creatinine or 
> 200 μg/min (microgram albumin per minute) or > 200 mg/24 h [milligram albumin per 24 hours] demonstrated in two out of three unrelated spot urine or timed samples in the last 24 months prior to randomization.
	
Measured 180 days prior to drug initiation in any diagnosis position in inpatient or outpatient filters:
 
CKD stage 3 and stage 4
 
585.3x-585.4x
	
CKD stage 1: GFR > 90 CKD stage 2: GFR 60 to 89 CKD stage 3a: GFR 45 to 59 CKD stage 3b: GFR 30 to 44 CKD stage 4: GFR 15 to 29 CKD stage 5: GFR < 15

EXCLUSION CRITERIA		

1) Type 1 diabetes mellitus.
	
Measured 180 days prior to drug initiation in any diagnosis position in inpatient or outpatient care setting:
 
DM type 1-At least 1 inpatient or outpatient ICD-9 Dx code of 250.x1 or 250.x3 or ICD-10 Dx code of E10.x in the 12 months prior to drug initiation. 6-months prior
	

2) Treatment (≥ 7 consecutive days) with GLP-1 receptor agonists, other DPP-4 inhibitors or SGLT-2 inhibitors prior to informed consent. Note: This also includes clinical trials where these antidiabetic drugs have been provided to the patient.
	
Measured 180 days prior to drug initiation as a dispensing for one of the following:
 
Treatment (≥ 7 days) with GLP-1 receptor agonists (lixisenatide, dulaglutide, albiglutide, tiraglutide, exenatide), other DPP-4 inhibitors (alogliptin, sitagliptin, saxagliptin) or SGLT-2 inhibitors (canagliflozin, dapagliflozin, empagliflozin) prior to CED
	

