Appendix A

Antidiabetic class	Specific agent	Notes
SGLT2-inhibitors	Canagliflozin	Approved 3/29/2013
	Dapagliflozin	
	Empagliflozin	
	Ertugliflozin	Approved Dec 21, 2017
2 nd generation sulfonylureas	Glimepiride	
	Glipizide	
	Glyburide	
DPP-4 inhibitors	Alogliptin	
	Linagliptin	
	Saxagliptin	
	Sitagliptin	
GLP-1 receptor agonist (GLP1-RA)	Exenatide	
	Liraglutide	
	Albiglutide	Approved April 15, 2014 and discontinued July 26, 2017
	Dulaglutide	Approved Sep 18, 2014
	Lixisenatide	Approved July 28, 2016
	Semaglutide	Approved Dec 5, 2017
Insulin	Insulin Aspart	
	Insulin Aspart/Insulin Aspart	
	Protamine	
	Insulin Degludec	
	Insulin Detemir	
	Insulin Glargine	
	Insulin Glulisine	
	Insulin human isophane (NPH)	
	Insulin human regular (search with NPH, don't want bf-pk)	
	Insulin human regular/ Insulin human isophane (NPH)	
	Insulin Lispro	

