Obesity; n (%)	16,061 (14.1%)	1,661 (18.7%)	10,204 (8.9%)	989 (11.3%)	37,005 (10.1%)	3,919 (11.7%)	63,270 (10.6%)	6,569 (12.9%)	-0.07
Overweight; n (%)	5,405 (4.7%)	591 (6.6%)	1,779 (1.6%)	164 (1.9%)	11,533 (3.1%)	1,342 (4.0%)	18,717 (3.2%)	2,097 (4.1%)	-0.05
Smoking; n (%)	12,866 (11.3%)	1,123 (12.6%)	6,558 (5.8%)	472 (5.4%)	48,039 (13.1%)	4,237 (12.7%)	67,463 (11.4%)	5,832 (11.4%)	0.00
Alcohol abuse or dependence; n (%)	0 (0.0%)	0 (0.0%)	0 (0.0%)	0 (0.0%)	0 (0.0%)	0 (0.0%)	#VALUE!	00 (0.0%)	#VALUE!
Drug abuse or dependence; n (%)	0 (0.0%)	0 (0.0%)	0 (0.0%)	0 (0.0%)	0 (0.0%)	0 (0.0%)	#VALUE!	00 (0.0%)	#VALUE!
COPD; n (%)	12,993 (11.4%)	882 (9.9%)	9,142 (8.0%)	618 (7.1%)	50,518 (13.8%)	4,685 (14.0%)	72,653 (12.2%)	6,185 (12.1%)	0.00

Table 1

Asthma; n (%)	5,959 (5.2%)	569 (6.4%)	5,213 (4.6%)	426 (4.9%)	22,404 (6.1%)	2,223 (6.7%)	33,576 (5.7%)	3,218 (6.3%)	-0.03
Obstructive sleep apnea; n (%)	9,320 (8.2%)	876 (9.8%)	10,424 (9.1%)	939 (10.7%)	22,520 (6.2%)	2,217 (6.6%)	42,264 (7.1%)	4,032 (7.9%)	-0.03
Pneumonia; n (%)	3,866 (3.4%)	318 (3.6%)	3,558 (3.1%)	241 (2.8%)	16,296 (4.5%)	1,507 (4.5%)	23,720 (4.0%)	2,066 (4.0%)	0.00
Imaging; n (%)	155 (0.1%)	17 (0.2%)	131 (0.1%)	7 (0.1%)	712 (0.2%)	54 (0.2%)	998 (0.2%)	78 (0.2%)	0.00
Diabetes Medications									
DM Medications - AGIs; n (%)	359 (0.3%)	32 (0.4%)	308 (0.3%)	32 (0.4%)	1,322 (0.4%)	202 (0.6%)	1,989 (0.3%)	266 (0.5%)	-0.03
DM Medications - Glitazones; n (%)	7,693 (6.7%)	617 (6.9%)	9,595 (8.4%)	839 (9.6%)	22,794 (6.2%)	2,478 (7.4%)	40,082 (6.7%)	3,934 (7.7%)	-0.04
DM Medications - Insulin; n (%)	15,753 (13.8%)	2,424 (27.2%)	15,075 (13.2%)	1,908 (21.8%)	55,854 (15.3%)	9,388 (28.1%)	86,682 (14.6%)	13,720 (26.9%)	-0.31
DM Medications - Meglitinides; n (%)	719 (0.6%)	184 (2.1%)	1,020 (0.9%)	248 (2.8%)	3,957 (1.1%)	1,190 (3.6%)	5,696 (1.0%)	1,622 (3.2%)	-0.15
DM Medications - Metformin; n (%)	67,785 (59.5%)	4,911 (55.2%)	68,989 (60.5%)	4,989 (57.1%)	211,773 (57.7%)	17,663 (52.9%)	348,047 (58.6%)	27,563 (54.0%)	0.09
Concomitant initiation or current use of SGLT2i; n (%)	222 (0.2%)	268 (3.0%)	167 (0.1%)	566 (6.5%)	259 (0.1%)	412 (1.2%)	#VALUE!	1,246 (2.4%)	#VALUE!
Concomitant initiation or current use of AGIs; n (%)	260 (0.2%)	26 (0.3%)	230 (0.2%)	23 (0.3%)	938 (0.3%)	134 (0.4%)	1,428 (0.2%)	183 (0.4%)	-0.04
Concomitant initiation or current use of Glitazones; n (%)	5,876 (5.2%)	424 (4.8%)	7,225 (6.3%)	527 (6.0%)	17,490 (4.8%)	1,741 (5.2%)	30,591 (5.1%)	2,692 (5.3%)	-0.01

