Concomitant initiation or current use of Insulin; n (%)	10,884 (9.5%)	1,862 (20.9%)	10,876 (9.5%)	1,443 (16.5%)	39,560 (10.8%)	7,259 (21.7%)	61,320 (10.3%)	10,564 (20.7%)	-0.29
Concomitant initiation or current use of Meglitinides; n (%)	453 (0.4%)	134 (1.5%)	655 (0.6%)	195 (2.2%)	2,488 (0.7%)	892 (2.7%)	3,596 (0.6%)	1,221 (2.4%)	-0.15
Concomitant initiation or current use of Metformin; n (%)	56,752 (49.8%)	3,913 (43.9%)	58,199 (51.0%)	3,978 (45.5%)	177,256 (48.4%)	13,934 (41.7%)	292,207 (49.2%)	21,825 (42.8%)	0.13
Past use of SGLT2i; n (%)	1 (0.0%)	0 (0.0%)	19 (0.0%)	1 (0.0%)	4 (0.0%)	0 (0.0%)	#VALUE!	001 (0.0%)	#VALUE!
Past use of AGIs; n (%)	99 (0.1%)	6 (0.1%)	78 (0.1%)	9 (0.1%)	384 (0.1%)	68 (0.2%)	561 (0.1%)	83 (0.2%)	-0.03
Past use of Glitazones; n (%)	1,817 (1.6%)	193 (2.2%)	2,371 (2.1%)	312 (3.6%)	5,304 (1.4%)	737 (2.2%)	9,492 (1.6%)	1,242 (2.4%)	-0.06
Past use of Insulin; n (%)	4,869 (4.3%)	562 (6.3%)	4,199 (3.7%)	465 (5.3%)	16,297 (4.5%)	2,129 (6.4%)	25,365 (4.3%)	3,156 (6.2%)	-0.09
Past use of Meglitinides; n (%)	266 (0.2%)	50 (0.6%)	365 (0.3%)	53 (0.6%)	1,469 (0.4%)	298 (0.9%)	2,100 (0.4%)	401 (0.8%)	-0.05
Past use of metformin; n (%)	11,033 (9.7%)	998 (11.2%)	10,790 (9.5%)	1,011 (11.6%)	34,017 (9.3%)	3,729 (11.2%)	55,840 (9.4%)	5,738 (11.2%)	-0.06
Other Medications									
Use of ACE inhibitors; n (%)	52,181 (45.8%)	3,676 (41.4%)	50,776 (44.5%)	3,495 (40.0%)	163,750 (44.7%)	12,790 (38.3%)	266,707 (44.9%)	19,961 (39.1%)	0.12
Use of ARBs; n (%)	28,284 (24.8%)	2,777 (31.2%)	28,769 (25.2%)	2,858 (32.7%)	97,329 (26.6%)	11,969 (35.8%)	154,382 (26.0%)	17,604 (34.5%)	-0.19
Use of Loop Diuretics; n (%)	20,910 (18.3%)	1,833 (20.6%)	19,444 (17.1%)	1,688 (19.3%)	88,445 (24.2%)	9,010 (27.0%)	128,799 (21.7%)	12,531 (24.6%)	-0.07
Use of other diuretics; n (%)	4,374 (3.8%)	435 (4.9%)	4,519 (4.0%)	441 (5.0%)	16,078 (4.4%)	1,632 (4.9%)	24,971 (4.2%)	2,508 (4.9%)	-0.03
Use of nitrates-United; n (%)	10,414 (9.1%)	772 (8.7%)	11,043 (9.7%)	747 (8.6%)	42,114 (11.5%)	3,874 (11.6%)	63,671 (10.7%)	5,393 (10.6%)	0.00
Use of other hypertension drugs; n (%)	10,825 (9.5%)	920 (10.3%)	9,771 (8.6%)	794 (9.1%)	37,611 (10.3%)	3,867 (11.6%)	58,207 (9.8%)	5,581 (10.9%)	-0.04
Use of digoxin; n (%)	3,374 (3.0%)	219 (2.5%)	3,676 (3.2%)	272 (3.1%)	16,616 (4.5%)	1,350 (4.0%)	23,666 (4.0%)	1,841 (3.6%)	0.02
Use of Anti-arrhythmics; n (%)	2,343 (2.1%)	176 (2.0%)	2,629 (2.3%)	216 (2.5%)	10,532 (2.9%)	1,055 (3.2%)	15,504 (2.6%)	1,447 (2.8%)	-0.01

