N antidiabetic drugs at index date									
...mean (sd)	1.76 (0.70)	1.75 (0.68)	1.77 (0.72)	1.77 (0.70)	1.73 (0.70)	1.73 (0.67)	1.74 (0.70)	1.74 (0.68)	0.00
...median [IQR]	2.00 [1.00, 2.00]	2.00 [1.00, 2.00]	2.00 [1.00, 2.00]	2.00 [1.00, 2.00]	2.00 [1.00, 2.00]	2.00 [1.00, 2.00]	2.00 (0.70)	2.00 (0.68)	0.00
number of different/distinct medication prescriptions									
...mean (sd)	11.06 (5.30)	11.07 (5.36)	10.74 (5.13)	10.66 (5.07)	11.45 (5.09)	11.45 (5.01)	11.26 (5.13)	11.25 (5.08)	0.00
...median [IQR]	10.00 [7.00, 14.00]	10.00 [7.00, 14.00]	10.00 [7.00, 13.00]	10.00 [7.00, 14.00]	11.00 [8.00, 14.00]	11.00 [8.00, 14.00]	10.65 (5.13)	10.65 (5.08)	0.00
Number of Hospitalizations									
...mean (sd)	0.13 (0.41)	0.13 (0.41)	0.12 (0.38)	0.12 (0.39)	0.17 (0.48)	0.16 (0.48)	0.15 (0.45)	0.15 (0.45)	0.00
...median [IQR]	0.00 [0.00, 0.00]	0.00 [0.00, 0.00]	0.00 [0.00, 0.00]	0.00 [0.00, 0.00]	0.00 [0.00, 0.00]	0.00 [0.00, 0.00]	0.00 [0.00, 0.00]	0.00 [0.00, 0.00]	0.00
Number of hospital days									
...mean (sd)	0.65 (2.51)	0.67 (2.66)	0.63 (2.74)	0.66 (2.86)	1.03 (3.87)	1.02 (3.97)	0.90 (3.49)	0.90 (3.60)	0.00
...median [IQR]	0.00 [0.00, 0.00]	0.00 [0.00, 0.00]	0.00 [0.00, 0.00]	0.00 [0.00, 0.00]	0.00 [0.00, 0.00]	0.00 [0.00, 0.00]	0.00 [0.00, 0.00]	0.00 [0.00, 0.00]	0.00
Number of Emergency Department (ED) visits									
...mean (sd)	0.50 (1.18)	0.49 (1.40)	0.19 (1.07)	0.19 (1.26)	0.63 (1.43)	0.63 (1.44)	0.53 (1.33)	0.53 (1.40)	0.00
...median [IQR]	0.00 [0.00, 0.00]	0.00 [0.00, 0.00]	0.00 [0.00, 0.00]	0.00 [0.00, 0.00]	0.00 [0.00, 0.00]	0.00 [0.00, 0.00]	0.00 [1.33]	0.00 [1.40)	0.00
Number of Office visits									
...mean (sd)	5.54 (4.50)	5.53 (4.36)	5.93 (5.53)	5.86 (4.31)	6.33 (4.88)	6.36 (4.75)	6.12 (4.93)	6.13 (4.61)	0.00
...median [IQR]	4.00 [2.00, 7.00]	5.00 [3.00, 7.00]	5.00 [3.00, 8.00]	5.00 [3.00, 8.00]	5.00 [3.00, 9.00]	5.00 [3.00, 9.00]	4.83 (4.93)	5.00 (4.61)	-0.04
Number of Endocrinologist visits									
...mean (sd)	0.69 (2.65)	0.80 (2.89)	0.72 (2.77)	0.83 (3.11)	0.94 (3.83)	0.94 (3.69)	0.86 (3.48)	0.90 (3.47)	-0.01
...median [IQR]	0.00 [0.00, 0.00]	0.00 [0.00, 0.00]	0.00 [0.00, 0.00]	0.00 [0.00, 0.00]	0.00 [0.00, 0.00]	0.00 [0.00, 0.00]	0.00 [3.48)	0.00 [3.47)	0.00
Number of internal medicine/family medicine visits									
...mean (sd)	10.20 (14.44)	9.35 (14.18)	7.99 (10.52)	7.84 (10.00)	8.97 (12.50)	8.98 (11.60)	9.02 (12.55)	8.85 (11.84)	0.01

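### Table 1 and the planned PS omit GLP-1 RA and other DPP-4 inhibitor use at cohort entry, and the balanced drug count after matching conceals different class mixes in the two arms

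*Combined protocol and SAP*

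**What the plan says.** Section 9 fixes the content of the PS by reference to Table 1: "The PS should include the complete list of covariates (excluding laboratory values, which are missing in some patients").

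In both panels of Table 1 (Appendix B), the concomitant-use rows run from "Concomitant initiation or current use of SGLT2i; n" through alpha-glucosidase inhibitors (AGIs), glitazones, insulin and meglitinides to "Concomitant initiation or current use of Metformin; n". Pramlintide and first-generation SUs have separate any-use rows. The list also carries the total, "N antidiabetic drugs at index date". The antidiabetic class sheet in Appendix A names "GLP-1 receptor agonist (GLP1-RA") and the DPP-4 inhibitors as classes, but neither Table 1 panel has a row for GLP-1 RA or for non-linagliptin DPP-4 inhibitors.

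Exclusion 2 in Appendix A removes prior users of GLP-1 RA, other DPP-4 inhibitors and SGLT2 inhibitors. Its window is "Measured 180 days prior to drug initiation as a dispensing for one of the following". For as-treated follow-up, Section 6.3.2 states: "An added treatment that is not part of the exposure or comparator group does not fulfill this criterion".

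**The concern.** A PS that contains the number of drugs but not all the classes can balance the number with the wrong classes. SU is the proxy for placebo, so class mix at entry matters. Another DPP-4 inhibitor in the SU arm would put the tested class in both arms and pull a non-inferiority hazard ratio toward 1. A GLP-1 RA would move it by whatever effect that class has on MACE.

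Exclusion 2 does not clearly prevent this, because it looks back from initiation and does not mention drugs started with the index drug. The table suggests that co-initiators remain. Concomitant SGLT2 inhibitor use is 3.0% (Optum) and 6.5% (MarketScan) of unmatched linagliptin patients, while past use is about zero. Such patients also stay in as-treated follow-up. Section 10 asks for balance to be judged from a table that cannot show these two classes.

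**Working it through.** **Inputs.** All are from Appendix B, Table 1, PS-matched panel: arm sizes 8,880 (Optum), 8,716 (MarketScan) and 33,319 (Medicare); the six concomitant-use counts; and the mean number of antidiabetic drugs at index.

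**Reproducing the printed pooled mean.** SU: (8,880 × 1.76 + 8,716 × 1.77 + 33,319 × 1.73) / 50,915 = 1.7421. Linagliptin, with 1.75, 1.77 and 1.73: 1.7403. Both are printed as 1.74.

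**Residual.** Residual drugs per patient = mean count − 1 (index drug) − sum of the six class proportions. Class counts are in the order SGLT2 inhibitor, AGI, glitazone, insulin, meglitinide, metformin. Means are printed to two decimals, so each residual carries ±0.005.

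| Arm, database | Sum of six classes | Proportion | Mean | Residual |
|---|---|---|---|---|
| SU, Optum | 51+31+427+1,806+118+4,016 = 6,449 | 0.7262 | 1.76 | 0.0338 |
| SU, MarketScan | 62+26+539+1,393+191+4,013 = 6,224 | 0.7141 | 1.77 | 0.0559 |
| SU, Medicare | 22+138+1,750+7,081+821+13,978 = 23,790 | 0.7140 | 1.73 | 0.0160 |
| Linagliptin, Optum | 267+26+423+1,841+129+3,909 = 6,595 | 0.7427 | 1.75 | 0.0073 |
| Linagliptin, MarketScan | 559+23+525+1,435+187+3,970 = 6,699 | 0.7686 | 1.77 | 0.0014 |
| Linagliptin, Medicare | 412+128+1,734+7,195+860+13,920 = 24,249 | 0.7278 | 1.73 | 0.0022 |

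Weighted by patients, this is 0.0259 for SU (0.021 to 0.031) and 0.0030 for linagliptin (at most 0.008). With rounding at its worst in both arms, 0.021 still exceeds 0.008. The same subtraction on the unmatched panel gives 0.0136 and 0.0011, so the gap grew from about 0.0125 to 0.023.

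**Can the any-use rows explain it?** Pramlintide plus first-generation SU total 0 + 4 = 4 matched SU patients in Optum (0.05%) and 10 + 2 = 12 in MarketScan (0.14%), against residuals of 0.034 and 0.056. The Medicare cells are suppressed.

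**The offset.** Matched concomitant SGLT2 inhibitor use is (51 + 62 + 22)/50,915 = 0.27% in the SU arm and 1,238/50,915 = 2.43% in the linagliptin arm, a standardized difference of about −0.19 (MarketScan −0.31). The pooled SU cell and the pooled standardized difference print #VALUE!. By database:

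| | SGLT2 inhibitor deficit in SU arm (points) | Residual excess in SU arm (points) |
|---|---|---|
| Optum | 2.4 | 2.6 |
| MarketScan | 5.7 | 5.4 |
| Medicare | 1.2 | 1.4 |

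**Effect on the hazard ratio.** Assume one residual drug per patient and equal baseline risk.
- If all were other DPP-4 inhibitors sharing linagliptin's effect, a true 1.30 reads 1.30/(1 + 0.0259 × 0.30) = 1.290 pooled (0.8% lower). In MarketScan it reads 1.30/(1 + 0.0559 × 0.30) = 1.279 (1.6% lower). At a true value near 1 the shift is close to nil.
- If all were GLP-1 RA with an illustrative MACE hazard ratio of 0.85 to 0.90 (an assumption, not in the documents), the ratio rises. At 0.85 the pooled factor is (1 − 0.0030 × 0.15)/(1 − 0.0259 × 0.15) = 1.0034; at 0.90 it is 1.0023. In MarketScan the rise is 0.5% to 0.8%.

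Neither calculation nets out the excess SGLT2 inhibitor use in the linagliptin arm.

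**The case against.** The strongest reply is that the residual is unidentified. The documents do not define the count, do not say that it is by class, and do not give it the same window as the concomitant-use rows. A second SU agent could be counted: Section 6.3.2 treats individual SUs as separate drugs, and the linagliptin arm, with a single index agent, cannot test this. That stands. The agreement with the SGLT2 inhibitor deficit does not settle it either. Once the count and the other five classes are balanced, any residual must roughly equal that deficit, whatever it consists of. What the linagliptin arm does show is that multiple insulins are not counted separately, since its residual is near zero with 20.6% on insulin. Even there the fit is not perfect: Optum's 0.0073 is outside the 0.005 rounding tolerance.

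A second reply is that SGLT2 inhibitors have a row and are still badly unbalanced, so a row does not secure balance. This also stands and bears on the fix. Linagliptin initiators with concomitant SGLT2 inhibitor use outnumber their SU counterparts in every database before matching (268 vs 222, 566 vs 167, 412 vs 259), yet 1,238 of the 1,246 were matched. This suggests, without proving it, that the row was not effectively in the fitted PS.

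Third, a reader might infer that 2.6% of SU patients entered on classes that the trial barred. The documents do not support this. The figure is drugs per patient, the class is inferred, and the bar concerns prior treatment. Section 5.1 allows other antidiabetic drugs during follow-up.

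Finally, the effect is small. Weighted by Section 10's expected events (294, 326 and 2,830), the SU residual is about 0.021 rather than 0.026.

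**Conclusion.** The point holds as a gap in covariate coverage with a measurable trace. Two classes named in Exclusion 2 have no row in Table 1, so on Section 9's rule they are not in the PS, while the drug count is. About 0.026 drugs per matched SU patient against 0.003 per linagliptin patient are not explained by the listed classes. Rounding does not remove the gap, and matching widened it. Read as a patient proportion, the pooled standardized difference is about 0.19, or about 0.11 with rounding at its worst; the largest printed pooled value on a matched non-laboratory row is 0.04. The equal means of 1.74 therefore do not show that the arms take the same drugs.

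This assumes that the count is one index drug plus one per class, on the same index-date definition as the rows. Co-initiated GLP-1 RA or other DPP-4 inhibitors are the likely source, but a second SU agent is not strictly excluded.

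It would be too strong to conclude that the hazard ratio is materially biased. The plausible shift is about 1% or less pooled and up to about 2% in MarketScan, with the direction set by the class. The correction is worth making because it is cheap and Section 13 carries no date for the comparative analysis.

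**What to change.** Before the comparative analysis:

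1. Define the drug count: by class or by agent, and in which window. Tabulate index-date GLP-1 RA and other DPP-4 inhibitor use by arm and database.
2. Add both as Table 1 rows and PS covariates alongside the count.
3. Confirm that concomitant SGLT2 inhibitor use is in the fitted PS, and correct the #VALUE! cells in that row.
4. Re-match in each database and report balance by class as well as for the count.
5. If any of the three classes stays unbalanced, repeat the analysis without those patients and report how many were removed. For SGLT2 inhibitors this is likely to be needed, given the short supply of SU users noted above.

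The cost is two covariates built from the existing class sheet and a re-run of the match. Removal would cost about 1 to 2% of SU initiators for the unlisted classes (0.0136 of 594,152 is about 8,080 if each carries one such drug; rounding range 0.9% to 1.9%). If SGLT2 inhibitor users also go, it costs about 2.4% of linagliptin initiators (1,246/51,041).

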5.1 Cohort Summary

This study will involve a new user, parallel group, cohort study design comparing linagliptin to the 2nd generation sulfonylurea (SU) antidiabetic class as a proxy for placebo. 2nd generation SUs are not known to have an impact on the outcome of interest. In addition, SUs were the most frequent background treatment in CARMELINA (after metformin), and DPP4i and SUs are preferentially prescribed to similarly older patients in real world (Paterno et al., 2019). The patients will be required to have continuous enrollment during the baseline period of 180 days before initiation of linagliptin or a comparator drug (cohort entry date). Follow-up for the outcome (3P-MACE), begins the day after drug initiation. As in the trial, patients are allowed to take other antidiabetic medications during study follow-up.

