Non-inferiority margin	1.3
Number of events expected	293.928
Power	0.613734405

- Marketscan

Non-inferiority Analysis	
Number of patients matched	
Reference	8,716
Exposed	8,716
Risk per 1,000 patients	18.7
Assumed HR from RCT	1
Alpha (2-sided)	0.05
Non-inferiority margin	1.3
Number of events expected	325.9784
Power	0.658551313

- Medicare

Non-inferiority Analysis	
Number of patients matched	
Reference	33,319
Exposed	33,319
Risk per 1,000 patients	42.47
Assumed HR from RCT	1
Alpha (2-sided)	0.05
Non-inferiority margin	1.3
Number of events expected	2830.11586
Power	0.99999974

- Stop analyses until balance and final power assessment are reviewed by primary investigators, FDA, and assigned members of advisory board. Reviewers evaluate the results of the analyses described above in Sections 9 and 10, including numbers of patients, balance in patient characteristics, follow-up time, and reasons for censoring by treatment group, as well as overall rates of outcomes and study power.

Reviewed by PI:	[name]	Date reviewed:	12/9/19
Reviewed by FDA:	[name]	Date reviewed:	12/20/19
Reasons for stopping analysis (if required):			

11. Study Confidence and Concerns

Deadline for voting on study confidence and listing concerns: 12/20/19

- If final feasibility and power analyses are reviewed and approved, proceed to the remaining protocol steps.
- All study team and advisory board members that review this protocol should at this stage provide their level of confidence for the success of the RWD study in the [Google Form](#). This form also provides space for reviewers to list any concerns that they feel may

contribute to a failure to replicate the findings of the RCT, including differences in study populations, poor measurement of study variables, or residual confounding. All responses will be kept confidential and individual-level results will only be shared with the individual respondent.

12. Register study protocol on clinicalTrials.gov

Date conducted:

- Register the study on [clinicalTrials.gov](https://clinicaltrials.gov) and upload this document.

13. Comparative Analyses

Action report name:

Date conducted:

13.1 For primary analysis:

- In the PS-matched cohort from Section 9, calculate the HR for each outcome for linagliptin versus referent patients using a Cox proportional hazards model.

13.2 For secondary analyses:

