Psychosis; n (%)	112 (1.3%)	129 (1.5%)	57 (0.7%)	55 (0.6%)	795 (2.4%)	792 (2.4%)	964 (1.9%)	976 (1.9%)	.00
Obesity; n (%)	1,752 (19.7%)	1,655 (18.6%)	1,002 (11.5%)	983 (11.3%)	3,985 (12.0%)	3,909 (11.7%)	6,739 (13.2%)	6,547 (12.9%)	.01
Overweight; n (%)	576 (6.5%)	587 (6.6%)	146 (1.7%)	164 (1.9%)	1,351 (4.1%)	1,340 (4.0%)	2,073 (4.1%)	2,091 (4.1%)	.00
Smoking; n (%)	1,147 (12.9%)	1,120 (12.6%)	445 (5.1%)	472 (5.4%)	4,307 (12.9%)	4,230 (12.7%)	5,899 (11.6%)	5,822 (11.4%)	.01
Alcohol abuse or dependence; n (%)	0 (0.0%)	0 (0.0%)	0 (0.0%)	0 (0.0%)	0 (0.0%)	0 (0.0%)	000 (0.0%)	000 (0.0%)	#DIV/0!
Drug abuse or dependence; n (%)	0 (0.0%)	0 (0.0%)	0 (0.0%)	0 (0.0%)	0 (0.0%)	0 (0.0%)	000 (0.0%)	000 (0.0%)	#DIV/0!
COPD; n (%)	947 (10.7%)	878 (9.9%)	636 (7.3%)	617 (7.1%)	4,686 (14.1%)	4,669 (14.0%)	6,269 (12.3%)	6,164 (12.1%)	.01

Table 1

Asthma; n (%)	572 (6.4%)	566 (6.4%)	453 (5.2%)	423 (4.9%)	2,227 (6.7%)	2,213 (6.6%)	3,252 (6.4%)	3,202 (6.3%)	0.00
Obstructive sleep apnea; n (%)	916 (10.3%)	873 (9.8%)	947 (10.9%)	934 (10.7%)	2,238 (6.7%)	2,212 (6.6%)	4,101 (8.1%)	4,019 (7.9%)	0.01
Pneumonia; n (%)	325 (3.7%)	313 (3.5%)	229 (2.6%)	240 (2.8%)	1,503 (4.5%)	1,501 (4.5%)	2,057 (4.0%)	2,054 (4.0%)	0.00
Imaging; n (%)	9 (0.1%)	17 (0.2%)	11 (0.1%)	7 (0.1%)	74 (0.2%)	54 (0.2%)	94 (0.2%)	78 (0.2%)	0.00
Diabetes Medications									
DM Medications - AGIs; n (%)	40 (0.5%)	32 (0.4%)	33 (0.4%)	32 (0.4%)	210 (0.6%)	194 (0.6%)	283 (0.6%)	258 (0.5%)	0.01
DM Medications - Glitazones; n (%)	625 (7.0%)	616 (6.9%)	856 (9.8%)	836 (9.6%)	2,492 (7.5%)	2,468 (7.4%)	3,973 (7.8%)	3,920 (7.7%)	0.00
DM Medications - Insulin; n (%)	2,377 (26.8%)	2,402 (27.0%)	1,870 (21.5%)	1,896 (21.8%)	9,270 (27.8%)	9,320 (28.0%)	13,517 (26.5%)	13,618 (26.7%)	0.00
DM Medications - Meglitinides; n (%)	171 (1.9%)	179 (2.0%)	249 (2.9%)	240 (2.8%)	1,105 (3.3%)	1,154 (3.5%)	1,525 (3.0%)	1,573 (3.1%)	-0.01
DM Medications - Metformin; n (%)	5,016 (56.5%)	4,907 (55.3%)	5,021 (57.6%)	4,978 (57.1%)	17,725 (53.2%)	17,642 (52.9%)	27,762 (54.5%)	27,527 (54.1%)	0.01
Concomitant initiation or current use of SGLT2i; n (%)	51 (0.6%)	267 (3.0%)	62 (0.7%)	559 (6.4%)	22 (0.1%)	412 (1.2%)	#VALUE!	1,238 (2.4%)	#VALUE!
Concomitant initiation or current use of AGIs; n (%)	31 (0.3%)	26 (0.3%)	26 (0.3%)	23 (0.3%)	138 (0.4%)	128 (0.4%)	195 (0.4%)	177 (0.3%)	0.02
Concomitant initiation or current use of Glitazones; n (%)	427 (4.8%)	423 (4.8%)	539 (6.2%)	525 (6.0%)	1,750 (5.3%)	1,734 (5.2%)	2,716 (5.3%)	2,682 (5.3%)	0.00

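### Concomitant SGLT2 inhibitor use stays unbalanced after propensity-score matching in all three databases (standardized difference -0.15 to -0.31), and the pooled cells that should show this contain a spreadsheet error

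*Combined protocol and SAP*

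**What the plan says.** Section 9 sets the content of the propensity score: "The PS should include the complete list of covariates (excluding laboratory values, which are missing in some patients". It then asks the analyst to "Report covariate balance after matching". It gives no numerical threshold for acceptable balance.

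Section 10 makes that report a stopping point: "Stop analyses until balance and final power assessment are reviewed by primary investigators, FDA, and assigned members of advisory board". Section 13.1 defines the primary analysis: "In the PS-matched cohort from Section 9, calculate the HR for each outcome". It names a Cox model and lists no covariates for it.

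Table 1 in Appendix B has one column of standardized differences, for the pooled data. In the matched part, the row "Concomitant initiation or current use of SGLT2i; n" prints counts for each database, a pooled linagliptin count of 1,238 (2.4%), and `#VALUE!` for both the pooled referent count and the pooled standardized difference. The same two cells fail in the unmatched part.

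Concomitant use breaks no eligibility rule as written. Exclusion 2 looks only at the 180 days before cohort entry, and Section 5.1 says: "As in the trial, patients are allowed to take other antidiabetic medications during study follow-up".

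**The concern.** The match is the only control for confounding in the primary analysis. A covariate left unbalanced by the match therefore stays unbalanced in the primary hazard ratio. Balance review is also a formal gate before outcomes are run, and the column that summarises balance for that gate has an error in the row with the largest pooled non-laboratory imbalance.

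The `#VALUE!` entries are not privacy suppression. The Medicare counts of 22 and 412 are printed, and masked Medicare cells elsewhere in the table show `**`.

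Two things are at stake: a small bias toward linagliptin if SGLT2 inhibitors lower the rate of the primary outcome, and whether the fitted propensity score contained every covariate that Section 9 requires.

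**Working it through.** **Inputs.** Counts come from the concomitant SGLT2 inhibitor rows of Table 1, unmatched and matched. Denominators come from the patient-number rows. Expected events are those in the Section 10 power tables.

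**Pooled counts.** Linagliptin: 267 + 559 + 412 = 1,238, and 1,238/50,915 = 2.4%, as printed. The missing referent count is 51 + 62 + 22 = 135, or 0.3%.

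**Formula.** Standardized difference = (p0 - p1) / sqrt{[p0(1-p0) + p1(1-p1)]/2}, with p0 for sulfonylurea and p1 for linagliptin. It reproduces printed pooled values:
- concomitant insulin, unmatched: 61,320/594,152 vs 10,564/51,041 gives -0.290 (printed -0.29);
- concomitant metformin, unmatched: 0.129 (printed 0.13);
- naive new user, matched: -0.041 (printed -0.04).

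**SGLT2 inhibitor row.**

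| | Matched, SU vs linagliptin | N per arm | After | Before |
|---|---|---|---|---|
| Optum | 51 vs 267 | 8,880 | -0.184 | -0.226 |
| MarketScan | 62 vs 559 | 8,716 | -0.311 | -0.360 |
| Medicare | 22 vs 412 | 33,319 | -0.146 | -0.145 |
| Pooled | 135 vs 1,238 | 50,915 | -0.189 | -0.209 |

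Matching removed little in the commercial databases and nothing in Medicare. The other five concomitant-use rows (insulin, meglitinides, metformin, alpha-glucosidase inhibitors, glitazones) are at most 0.024 in absolute value in any database.

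**Scarcity of sulfonylurea co-users.** Before matching there are 222 + 167 + 259 = 648 on sulfonylurea and 268 + 566 + 412 = 1,246 on linagliptin. That is 0.83, 0.30 and 0.63 per linagliptin co-user in Optum, MarketScan and Medicare. The match kept 1,238 of the 1,246 linagliptin co-users but used only 135 of the 648 sulfonylurea co-users (51 of 222, 62 of 167, 22 of 259). If every sulfonylurea co-user were matched, the best attainable differences would be:
- Optum, 222 vs 267: -0.03;
- MarketScan, 167 vs 559: -0.23;
- Medicare, 259 vs 412: -0.05.

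Scarcity explains much of MarketScan but not the other two.

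**Was the covariate left out of the score?** At the unmatched sulfonylurea prevalence, the matched referents would contain:
- Optum: 222/113,991 x 8,880 = 17.3 (observed 51);
- MarketScan: 167/114,025 x 8,716 = 12.8 (observed 62);
- Medicare: 259/366,136 x 33,319 = 23.6 (observed 22).

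Medicare looks unselected on this covariate; Optum and MarketScan are enriched. The cause is not established.

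**Size of bias.** Suppose concomitant use multiplies the outcome hazard by h, the same in both arms (an assumption). The hazard ratio is then multiplied by [1 + p1(h-1)]/[1 + p0(h-1)].

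| h | Optum | MarketScan | Medicare | Pooled |
|---|---|---|---|---|
| 0.9 | 0.998 | 0.994 | 0.999 | 0.998 |
| 0.8 | 0.995 | 0.989 | 0.998 | 0.997 |
| 0.5 | 0.988 | 0.971 | 0.994 | 0.991 |

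Pooling weights the log factors by the database event counts, 294 + 326 + 2,830 = 3,450. The standard error of the log hazard ratio is about 2/sqrt(3,450) = 0.034, so the pooled shift is 0.05 to 0.25 standard errors. The pooled power table prints 2,638 events instead; that gives 2/sqrt(2,638) = 0.039 and at most 0.0086/0.039 = 0.22.

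**A second imbalance hidden by pooling.** Optum age 65-74 after matching is 3,436 vs 2,634 of 8,880 (38.7% vs 29.7%), a difference of 0.19 (0.20 before). Age 55-64 is 1,986 vs 2,434, or -0.12. The pooled column shows 0.04 and -0.04, and mean age in Optum is 66.96 in both arms.

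**The case against.** The strongest reply is that this hardly matters for the answer. The gap is 0.3% vs 2.4% pooled, about 82% of expected events (2,830 of 3,450) come from Medicare where the gap is 1.2 percentage points, and even an implausibly strong SGLT2 inhibitor effect moves the pooled estimate by a quarter of a standard error. This stands, and it limits the weight of the point.

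Nothing was concealed either. All six database-level counts are printed in the same row, and the linked balance reports, which are not in the document, may have shown more. This stands in part: a careful reader could see the imbalance, but the summary column would not show it.

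The plan sets no threshold for balance, so calling -0.15 unbalanced follows convention. That is true, but the contrast with the other concomitant-use rows does not need a threshold.

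The comparison with unmatched prevalence is a weak test of omission, because matched referents were chosen to resemble linagliptin users on many correlated covariates. That stands; no departure from Section 9 is shown. The best-case figures also assume that every sulfonylurea co-user can be matched, so they are limits and not forecasts.

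Finally, the table seems to compute differences from rounded percentages. For example, "Concomitant initiation or current use of AGIs; n" prints 0.02 pooled where the counts give 0.006. On that basis the missing cell would be -0.18, not -0.19. The distinction changes nothing of substance.

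**Conclusion.** The concern holds. After matching, concomitant SGLT2 inhibitor use differs by -0.18, -0.31 and -0.15 in the three databases and by -0.19 pooled, about nine times as common with linagliptin. The pooled figure that should report this is a spreadsheet error. These values follow directly from printed counts.

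The effect on the primary conclusion is small: a pooled factor of 0.998 to 0.991, and at worst 0.971 in MarketScan, for assumed hazard ratios of 0.9 to 0.5. This alone would not decide a 1.3-margin comparison.

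Whether the covariate was omitted from the propensity score cannot be told, because the fitted model is not shown. The point should be fixed because Section 13.1 has no later adjustment, and the repair is cheap while the Section 13 date is blank and no comparative result is recorded.

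**What to change.** Before any outcome analysis:

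1. Fill the matched pooled cells: referent 135 (0.3%), standardized difference -0.19 from counts. State whether the column is computed from counts or from rounded percentages. Correct the same two cells in the unmatched part to 648 (0.1%) and -0.21.
2. Check the fitted propensity score in each database against the Section 9 covariate list and state the result. Re-match if this covariate was left out. Optum and Medicare have room to improve; MarketScan stays at -0.23 at best while its linagliptin co-users are kept.
3. Prespecify, at least as a sensitivity analysis, a re-matched comparison restricted in both arms to patients without concomitant SGLT2 inhibitor use at index.
4. Print standardized differences within each database. For Optum, check how age enters the score and re-match if the age categories remain unbalanced.

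**Cost.** Items 1, 2 and 4 are table repairs and a model check. A re-match, if needed, changes the matched numbers, Table 1 and the power tables, so the Section 10 review would have to be repeated.

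The restricted analysis loses at most 1,246 of 51,041 linagliptin patients (2.4%; 566 of 8,736, or 6.5%, in MarketScan) and 648 of 594,152 sulfonylurea patients (0.1%). Power by the formula Phi(sqrt(D/4) x ln 1.3 - 1.96), with D the expected events, reproduces the Section 10 values. Removing the matched linagliptin co-users and one referent for each gives:
- Optum: D = 2 x 8,613 x 0.01655 = 285, power 0.614 to about 0.60;
- MarketScan: D = 2 x 8,157 x 0.0187 = 305, power 0.659 to about 0.63;
- Pooled, at the protocol's 25.91 per 1,000: D = 2 x 49,677 x 0.02591 = 2,574, power still above 0.999.
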